The Effect of Placement of A Support Under Shoulders on Laryngeal Visualization With C- Mac Miller Video Laryngoscope in The Children Younger Than Two Years Of Age

[name],

Title: Specialist anaesthesia

Affiliation: Department of Anaesthesiology and Reanimation, Inonu University, School of Medicine, Malatya, Turkey

Email: [contact]

[name],

Title: Professor

Affiliation: Department of Anaesthesiology and Reanimation, Inonu University, School of Medicine, Malatya, Turkey

Email: [contact]

[name],

Title: Associate professor

Affiliation: Department of Anaesthesiology and Reanimation, Inonu University, School of Medicine, Malatya, Turkey

Email: [contact]

[name]

Title: Professor

Affiliation: Department of Biostatistics, and Medical Informatics, Inonu University, School of Medicine, Malatya, Turkey

Email: [contact]

Corresponding Author:

[name]

Department of Anaesthesiology and Reanimation, Inonu University, School of Medicine, Malatya, Turkey

[contact]

[contact]/

[contact]

Conflicts of Interest: **None**

Study Protocol

Patient Selection

This study was approved by the University's Institutional Review Board (IRB #2016/203) and written informed consent will be obtained from the parents of the children participating in the trial. This study will be conducted in compliance with the Good Clinical Practice guidelines and adheres to the applicable Consolidated Standards of Reporting Trials (CONSORT) guidelines.

96 children younger than two years of age who were classified as ASA I or II and will be scheduled for the elective surgery necessitating endotracheal intubation under general anesthesia in hospital of Inonu University Faculty of Medicine will be included in the study.

Children who had an upper respiratory tract infection in the last 4 weeks and who expected to have difficult airway in the preoperative evaluation or who will not be stable during intubation (due to underlying respiratory or cardiovascular problems), will be excluded from the study.

Randomization

The present study will be planned as a prospective and randomized clinical trial. Randomization will be performed using the MedCalc package program (www.medcalc.org). A total of 96 cases will be randomly divided into two groups. The cases will be intubated by placing a folded towel under the shoulder named as Group 1 (n=48), and the cases will be intubated without placement of folded towel named as Group 2 (n=48).

Intubation Protocol

Age, gender, height, weight, ASA values and preoperative airway evaluation will be noted before the children will be taken to the operating room. No premedication was applied to the children. Intraoperative monitoring was provided with ECG, non-invasive blood pressure, capnography and pulse oximetry. The induction of general anesthesia will be achieved with sevoflurane (5% -8%) or thiopental (5-8 mg.kg⁻¹ IV) and fentanyl (1 µg.kg⁻¹ IV) in all children. After confirming mask ventilation, rocuronium (0.6 mg / kg⁻¹ IV) will be administered in order to facilitate endotracheal intubation. During mask ventilation, shoulders of the children in Group 1 will slightly be raised with a folded towel, in the children of Group 2, folded towel will not be placed under shoulder.

Tracheal intubation will be performed using C-MAC Miller VL, after muscle relaxation will be confirmed using a neuromuscular monitoring (Organon, Dublin, Ireland). Uncuffed spiral Endotracheal tube (ETT) with stylet and appropriate size for age of children, will be used in all patients. All tracheal intubations will be performed by a single anesthesiologist who performed more than 50 tracheal intubations with C-MAC Miller VL in children.

Study Outcomes

In our study, the primary outcome will be the POGO score. The percentage of glottis opening (POGO) score corresponds to the percentage of visualization of the glottis. A POGO score of 100% refers to the visualization of entire glottis opening from the anterior commissure of the vocal cords to the interarytenoid notch. If no part of the glottis opening is visible, the POGO

score is 0%. For the subsequent evaluation of a researcher who was blind to the position of the cases, screenshots of glottis will be taken during laryngoscopy with C-MAC Miller VL.

The secondary outcomes in the study will be the ease of use of the C-MAC VL device, the Cormack-Lehane Scores, the time to intubation, the number of intubation attempts, the optimization procedures during the endotracheal intubation and the complications.

The ease of use of the device in this position will be evaluated with a VAS score ranging from 0 (the most difficult and disturbing use) to 10 (easiest and most comfortable use) by anesthetist who used the C-MAC Miller VL device.

The time to intubation will be recorded as from the time C-MAC Miller VL entered the oral cavity until the time the end-tidal CO₂ (EtCO₂) trace was seen in the capnography. If intubation failed, the time of each attempt will be collected and more than three attempts will not be allowed.

The optimization procedures required for successful endotracheal intubation will be recorded as external laryngeal compression (displacement of the larynx by backward, upward and rightward pressure on the thyroid cartilage, or BURP) and position change (the rotation or vertical lifting of C-MAC Miller VL).

Complications including desaturation (peripheral oxygen saturation <90%), esophageal intubation, dental and mucosal damage will be noted.

Statistical Analysis

The primary outcome of our study is the POGO score. Based on the study of Kim et al. (8); when the estimated POGO score difference between two groups was 20, standard deviation was 34, type 1 error (alpha) 0.05 was and type 2 error (beta) was 0.20 (power = 0.80), the required sample size consisting of at least 94 patients (at least 47 in each group) was calculated by power analysis.

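### Does the exclusion for instability during intubation let children be dropped after randomisation and bias the comparison?

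*Combined protocol and SAP*

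**What the plan says.** The exclusions stand in one sentence under Patient Selection. The first is an upper respiratory infection in the preceding four weeks. The second covers children "who expected to have difficult airway in the preoperative evaluation". The third covers those "or who will not be stable during intubation (due to underlying respiratory or cardiovascular problems), will be excluded from the study". The eligible population is "96 children younger than two years of age who were classified as ASA I or II", scheduled for elective surgery.

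The Randomization section follows: "A total of 96 cases will be randomly divided into two groups", 48 to each. It does not say when allocation takes place relative to the eligibility check or to induction.

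Under Intubation Protocol the intervention comes before laryngoscopy: "During mask ventilation, shoulders of the children in Group 1 will slightly be raised with a folded towel".

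Under Study Outcomes, the time of each attempt is collected when intubation fails, up to three attempts. The safety record reads: "Complications including desaturation (peripheral oxygen saturation <90%), esophageal intubation, dental and mucosal damage will be noted".

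Statistical Analysis contains only the sample-size calculation. It names no analysis population.

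**The concern.** The difficult-airway criterion carries a word of prediction and a time of assessment. The instability criterion carries neither, and its only time reference is the intubation itself. By then the child has been allocated and positioned, and the towel is visible in theatre. The only blinding described is that of the researcher who later reads the screenshots.

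On that literal reading, one event, such as a fall in saturation at laryngoscopy, could count either as a complication or as grounds for removal. No sentence says that every randomised child is analysed in the assigned group.

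If children with a poor view and long attempts were the ones removed, and more of them came from the arm with the worse position, low POGO scores, long intubation times and desaturations would disappear unevenly. The difference between arms would probably shrink and harm would be undercounted. Extra recruitment would not repair that, because the loss would depend on outcome.

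**Working it through.** **1. The plan's own figure.** The inputs from Statistical Analysis are a difference of 20 POGO points, SD 34, alpha 0.05 and power 0.80. Sidedness is not stated.

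- Normal approximation, two-sided: n per group = 2 × [34 × (1.960 + 0.842) / 20]² = 45.4, rounded up to 46.
- Two-sample t-test, two-sided: 46.35, rounded up to 47 per group, or 94 in total. This matches the plan.
- One-sided versions give 36 to 37 per group and do not match, so the test is taken as two-sided.

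T-test power is 81.4% at 48 per group, 80.6% at 47 and 79.7% at 46. The 96 children leave room to lose one per group.

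**2. What the wording covers.**

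| Feature of the text | Forecast before enrolment | Event seen after allocation |
|---|---|---|
| Under Patient Selection, ahead of Randomization | fits | does not fit |
| Same sentence as two criteria known before surgery | fits | does not fit |
| Limited to underlying respiratory or cardiovascular problems | fits: these already exist | fits only if the cause in theatre is that disease |
| Desaturation and failed attempts recorded as outcomes | fits | conflicts |
| Time reference is the intubation; no word of prediction | loose | fits |

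The bracketed cause matters most. The feared chain runs from poor view to repeated attempts, then instability, then exclusion. Instability that arises from the attempts is not caused by underlying disease, so even the literal text does not exclude those children. Verb form is weak evidence in a document that mixes tenses throughout.

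**3. Size if children were nevertheless dropped selectively.** The following values are assumptions, not in the documents: the no-towel arm has mean POGO 60, the dropped children average 20, all come from that arm, the true difference is 20 and the SD stays at 34. Dropping k of 48 gives a new mean of (48 × 60 − 20k) / (48 − k). This is a shift of 40k / (48 − k).

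| k | New mean | Shift | Remaining difference | Power, selective loss | Power, random loss |
|---|---|---|---|---|---|
| 0 | 60.0 | 0 | 20.0 | 81.4% | 81.4% |
| 2 | 2840/46 = 61.7 | 1.7 | 18.3 | 73.1% | 80.5% |
| 3 | 2820/45 = 62.7 | 2.7 | 17.3 | 68.1% | 80.1% |
| 4 | 2800/44 = 63.6 | 3.6 | 16.4 | 62.6% | 79.6% |

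With k = 4, power falls by 18.8 points under selective loss (81.4 − 62.6) and by 1.8 points under random loss (81.4 − 79.6). Nearly all the damage is the assumed selection.

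**4. A range for the assumed gap.** Let the dropped children lie g points below their arm's mean, so that the shift is k × g / (48 − k). The error column is the two-sided 5% error when there is no true difference, with standard error 34 × √(1/48 + 1/(48 − k)).

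| k | Shift, g = 34 (1 SD) | Error | Shift, g = 68 (2 SD) | Error |
|---|---|---|---|---|
| 1 | 0.7 | 5.1% | 1.4 | 5.5% |
| 3 | 2.3 | 6.2% | 4.5 | 9.9% |
| 5 | 4.0 | 8.6% | 7.9 | 19.8% |

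The large entries need five removals, all from one arm, of children with extreme scores. If equal numbers with the same gap were lost from both arms, the shifts would cancel.

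**The case for a change.** The best case for acting is that nothing in the plan closes the gap. The baseline items noted before theatre include ASA class and an airway evaluation, but no specific check of respiratory or cardiovascular stability, so no preoperative step is named at which the criterion is applied. Nor does the plan say who judges it, whether a randomised child may be excluded, or which children are analysed. A protocol that declares adherence to CONSORT might be expected to say so. Two sentences would settle the matter without more patients or any change in care. Complications are counts, so each child removed could be an event lost.

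The silences are real. It does not follow that the plan permits outcome-dependent exclusion in any practical sense. A preoperative assessment of a child under two that assigns an ASA class already takes account of cardiac and respiratory disease, so the step exists even though it is not linked to the criterion. It is an inference, not a statement in the documents, that staff aware of the allocation would make the judgement. The missing analysis-population sentence would be missing whatever this criterion said. Analysing randomised children in their assigned groups is the ordinary default, and it is what a statistician would do here.

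**Conclusion.** The concern does not hold as a flaw in the design. On its natural reading the criterion is a forecast, made at selection, of instability from existing disease. Applied that way, it removes no child after allocation and gives a sound comparison. The stated sample size reproduces at 94.

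What remains is unstated detail: the time of assessment for one criterion and a named analysis population. Sensible practice fills both, and writing them down would not alter the design, the analysis or the number of children.

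The possible bias cannot be sized from the documents, which give no exclusion rate and no arm means. The shifts of 1.7 to 3.6 points, against a planned difference of 20, rest wholly on assumed one-arm removal of children with assumed POGO scores. The conclusion depends on reading the criterion as a forecast. It would change if children were in fact withdrawn after towel placement because of how intubation went.

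### Optional improvement: have the same position-blind researcher score each stored screenshot twice, use the mean as the primary POGO value, and report intra-reader reliability

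*Combined protocol and SAP*

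**What the plan says.** Study Outcomes names the endpoint: "In our study, the primary outcome will be the POGO score". It defines the scale: "The percentage of glottis opening (POGO) score corresponds to the percentage of visualization of the glottis". The 100% and 0% anchors are given, the upper one being a view of the whole opening from the anterior commissure to the interarytenoid notch. The same paragraph says how the images are handled: "For the subsequent evaluation of a researcher who was blind to the position of the cases, screenshots of glottis will be taken". The reader is in the singular and is masked to position.

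The protocol does not state the number of readings per image, whether the percentage is estimated by eye or measured on the screen, how many screenshots are kept per child, or how repeatable the reading is. It mentions no second reading, second reader or averaging.

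Statistical Analysis bases the sample size on a cited earlier study: "when the estimated POGO score difference between two groups was 20, standard deviation was 34", with alpha 0.05 and power 0.80, giving at least 47 per group. The SD is a single total figure, not split into variation between children and reading error. Randomization plans 48 per group.

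**The concern.** POGO is a percentage of a span that may not be fully on the image. When part of the opening is out of view, the reader has to judge the full length, and no scoring rule or measuring tool is described. Some random reading error in the primary endpoint is therefore plausible. It would widen the interval for the towel effect without telling us anything about the towel.

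Part of that error can be removed after the event, because the images are stored and a masked reader is already assigned. The sample size has little slack (96 planned against a minimum of 94), so precision that needs no further children is worth having. Separately, a single reading would leave the trial unable to report how repeatable its own primary measurement is, which matters most if the result is null or borderline.

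**Working it through.** **Inputs from the documents.** Difference 20, SD 34, alpha 0.05, power 0.80, stated minimum 47 per group (Statistical Analysis); 48 per group planned (Randomization). The documents do not state sidedness.

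**Inputs assumed.** Intra-reader ICC of 0.95, 0.90 or 0.80; or, in the second scenario, a reading-error SD of 10 or 15. The documents give neither.

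**Step 1: reproduce the plan's figure.**
- Normal approximation, two-sided: n per arm = 2 × [34 × (1.960 + 0.842) / 20]² = 45.4, rounded up to 46 (92 in total).
- Two-sided two-sample t-test (noncentral t): 46.35, rounded up to 47 (94 in total), an exact match.
- One-sided (normal approximation): 36 per arm, which does not match.

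The two-sided t-test is used from here on. At 48 per arm its power is 0.814. The standard error is 34 × √(2/48) = 6.94, so the 95% interval half-width is 1.986 × 6.94 = 13.8 points.

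**Step 2: SD 34 assumed to include single-reading error.** With independent reading errors of equal variance, the SD of the mean of two readings is 34 × √[(1 + ICC)/2]. The implied error SD of one reading is 34 × √(1 − ICC).

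| Assumed ICC | Error SD, one reading | SD, mean of two | Power at 48 per arm | 95% half-width | n per arm for 80% power |
|---|---|---|---|---|---|
| 1.00 (perfectly repeatable) | 0 | 34.0 | 0.814 | 13.8 | 47 |
| 0.95 | 7.6 | 33.6 | 0.823 | 13.6 | 46 |
| 0.90 | 10.8 | 33.1 | 0.833 | 13.4 | 45 |
| 0.80 | 15.2 | 32.3 | 0.852 | 13.1 | 42 |

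The gains in power are 0.9, 1.9 and 3.8 percentage points. They are upper bounds at each ICC: if the reader remembers the images, the two errors are correlated and less is averaged out.

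**Step 3: reading error assumed to come on top of SD 34.** One reading has SD √(34² + e²); the mean of two has SD √(34² + e²/2).
- e = 10: SD 35.44 falls to 34.73, and power goes from 0.781 to 0.797.
- e = 15: SD 37.16 falls to 35.62, and power goes from 0.742 to 0.777.

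In this scenario a single reading falls short of the planned 80%, and the second reading recovers part of the shortfall but not all of it.

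**The case against.** The strongest reply is that nothing here is broken. The reader is masked to position, the sample size reproduces, and 96 children meet the plan's own power target. Random error in a masked reader costs only a little precision, and most of an SD of 34 would be variation between children that re-reading cannot touch. All of that stands, and it is why the point is optional.

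A reader might infer that the plan has each image read once and judged by eye. The documents say neither. They are silent on the number of readings and on the method, and a score measured on the image may carry little error. A reader might also take it as given that reading error is already part of the SD of 34. That figure comes from a cited study whose reading procedure the protocol does not describe. If readings were averaged there, the figure already holds some of the benefit; if it contains no reading error, Step 3 applies instead. Both scenarios are therefore shown, and neither is established.

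It is also fair to object that a second reading by the same person removes only that person's random error. Systematic error and the choice of screenshot stay as they were, and a high intra-reader ICC would not show that the scores are accurate. A second independent reader would address more but needs more staff.

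The objection does not reach two points. Averaging two readings of equal error variance cannot worsen precision, and without a repeat reading the repeatability of the primary endpoint goes unreported.

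**Conclusion.** This is a low-cost improvement, not a defect. The stronger inference, that the trial is underpowered or its sample size wrong because of reader noise, is not supported: 94 reproduces exactly and 96 give about 81% power on the plan's own inputs.

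If SD 34 includes single-reading error and the two errors are independent, averaging adds at most about 1 to 4 percentage points of power for an ICC between 0.95 and 0.80, and narrows the interval half-width by 0.2 to 0.7 of a POGO point. If reading error adds to SD 34, the gain is 1.6 points at an error SD of 10 and 3.5 points at 15. The size rests wholly on an undocumented ICC or error SD; it shrinks with recall and vanishes for a perfectly repeatable reader. The reliability estimate is a benefit whichever scenario holds.

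**What to change.** Add to Study Outcomes, before any image is scored, that:
- the same position-blind researcher scores every stored screenshot twice, the second time in a fresh random order, at least two weeks after the first and without sight of the first scores;
- the mean of the two readings is the primary POGO value;
- the intra-reader ICC is reported.

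The same passage should state how the percentage is obtained, by eye or by measurement.

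The cost is about 96 extra readings (taking one screenshot per child), a few hours for the researcher already assigned, and a short delay before analysis. It needs no additional staff, patients or procedures.

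### Does time to intubation need a stated rule for children who need more than one attempt?

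*Combined protocol and SAP*

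**What the plan says.** The combined protocol and SAP defines the outcome in Study Outcomes: "The time to intubation will be recorded as from the time C-MAC Miller VL entered the oral cavity until the time the end-tidal" CO₂ "trace was seen in the capnography". The next sentence reads: "If intubation failed, the time of each attempt will be collected and more than three attempts will not be allowed".

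The list of secondary outcomes in the same section includes "the time to intubation, the number of intubation attempts, the optimization procedures during the endotracheal intubation and the complications", so attempts are counted as an outcome of their own.

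Two other provisions limit how often a failed attempt should occur. Patient Selection excludes children "who expected to have difficult airway in the preoperative evaluation". The Intubation Protocol states: "All tracheal intubations will be performed by a single anesthesiologist who performed more than 50 tracheal intubations with C-MAC Miller VL in children".

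The Statistical Analysis section covers only the POGO sample size and does not mention time to intubation.

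**The concern.** The CO₂ trace is the only stop event given, and a failed attempt does not reach it. The plan therefore asks for a duration whose end it does not define. Three questions stay open:

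- When does a failed attempt stop?
- For a child with two or three attempts, is the analysed value the elapsed time from first entry, the sum of the attempt times, or the time of the last attempt?
- What value goes to a child not intubated after three attempts?

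The intervention changes positioning in order to change the laryngeal view, so attempt success could plausibly differ by arm. If it does, the three values give different between-arm comparisons, and a choice made after the times are seen could be challenged. The operator knows whether the towel is in place; blinded assessment is described only for the glottis screenshots.

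**Working it through.** The plan gives no figure for this outcome. Its one calculation, for POGO (difference 20, SD 34, alpha 0.05 taken as two-sided, power 0.80), reproduces: the two-sample t-test needs 46.35, rounded up to 47 per group, 94 in all. Nothing below affects it.

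**Assumed inputs (none is in the documents).** Successful attempt: mean 25 s in one arm and 30 s in the other. Failed attempt f = 40 s (range 20 to 60). Gap between attempts g = 60 s (range 30 to 120). Failure probability p per attempt: 1% to 10%.

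**One child.** One failed attempt and then a 25 s success gives 25 s (last attempt), 40 + 25 = 65 s (summed), or 40 + 60 + 25 = 125 s (elapsed).

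**How many children.** Of 96:

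| p | failed first attempt, 96p | chance of none, (1−p)^96 | never intubated, 96p³ |
|---|---|---|---|
| 1% | 1.0 | 38% | 0.0001 |
| 2% | 1.9 | 14% | 0.0008 |
| 5% | 4.8 | 0.7% | 0.012 |
| 10% | 9.6 | close to 0 | 0.096 |

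The value for a never-intubated child is close to a theoretical question.

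**Effect on means.** Expected failed attempts before the last permitted one are e(p) = p + p², so e(0.01) = 0.0101, e(0.02) = 0.0204, e(0.05) = 0.0525 and e(0.10) = 0.11. For the 30 s arm minus the 25 s arm:

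- last attempt: 5
- summed: 5 + [e(slow) − e(fast)] × f
- elapsed: 5 + [e(slow) − e(fast)] × (f + g)

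| failure, slow vs fast arm | summed | elapsed |
|---|---|---|
| 5% vs 1% | 5 + 0.0424 × 40 = 6.7 s | 5 + 0.0424 × 100 = 9.2 s |
| 1% vs 5% | 5 − 0.0424 × 40 = 3.3 s | 5 − 0.0424 × 100 = 0.8 s |
| 10% vs 2% | 5 + 0.0896 × 40 = 8.6 s | 5 + 0.0896 × 100 = 14.0 s |
| 2% vs 10% | 5 − 0.0896 × 40 = 1.4 s | 5 − 0.0896 × 100 = −4.0 s |

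Over the ranges of f and g, the 5% vs 1% row runs from 5.8 to 7.5 s (summed) and 7.1 to 12.6 s (elapsed). The 1% vs 5% row runs from 4.2 to 2.5 s and from 2.9 to −2.6 s.

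With equal failure rates but failed attempts of 30 s vs 50 s, the summed difference moves by e(p) × 20: 0.2 s at 1%, 1.1 s at 5%, 2.2 s at 10%. All three values agree only if failure rates, failed-attempt durations and gaps are equal in the two arms.

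**Effect on medians.** These means are driven by a few children carrying large additions. In the same model (lognormal times, SD 8 s, f = 40, g = 60), the last-attempt median difference is 5.2 s. Summed and elapsed times both give 5.6 s (5% vs 1%), 4.8 s (1% vs 5%), 6.1 s (10% vs 2%) and 4.3 s (2% vs 10%). The median shift is 0.4 to 0.9 s, the sign does not reverse, and summed and elapsed cannot be told apart.

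**Power of a rank test (simulated Mann-Whitney, 48 per arm).** With equal failure rates, last-attempt against elapsed power is 89% vs 88% at 1%, 90% vs 87% at 2%, 89% vs 82% at 5% and 89% vs 73% at 10%. If the faster arm fails more often, elapsed power is about 0.76 (5% vs 1%) or 0.54 (10% vs 2%), against about 0.89 for last-attempt time.

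**The case for a change.** The best case for a change is that it would cost two or three sentences and settle a choice that otherwise falls to an analyst who can see the data. The start of the clock is not tied to the first entry, and the following sentence switches to attempt times without saying how they combine. Accepting elapsed time still leaves the end of a failed attempt undefined. An analysis rule can be written late, but times that were never recorded may not be recoverable. With unequal failure rates, the rank-test power above shows that the choice is not harmless.

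Most of the facts here stand: the three items are unstated, and the effect is not nil. The demand for an amendment does not stand.

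- The stated start and stop events, applied as written, give one sound value for any child eventually intubated. The attempt sentence adds data and does not replace that definition.
- Attempt times must be collected in any case. A competent team would end a failed attempt when the device is withdrawn, and last-attempt and summed times could then be derived.
- Elapsed time charges failed attempts to the arm in which they occur; last-attempt time sets them aside and has somewhat more power in the assumed model. Either is defensible when shown beside the number of attempts.
- Failures cannot be hidden by the choice, because attempts are reported separately.

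It would also go too far to infer from "Complications including desaturation (peripheral oxygen saturation <90%), esophageal intubation, dental and mucosal damage will be noted" that the plan expects failures. Listing an event to be recorded is not a forecast.

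**Conclusion.** The concern describes missing detail correctly, but it does not call for a change to the plan. The literal definition supplies a usable value, the attempt data and attempt counts are collected, and choosing among the three values is a fair trade-off that analysts can make sensibly and report.

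The size cannot be known from the documents. Under the assumptions above, a 5% vs 1% imbalance moves the elapsed mean difference by 4.2 s in either direction and the median difference by about 0.4 s. A reversed sign appears only in means: at 2% vs 10% with the central times, or at 1% vs 5% with the longest assumed times. A 10% vs 2% imbalance means about 5 against 1 failed first attempts in 48 per arm (48 × 0.10 = 4.8; 48 × 0.02 = 0.96). Nothing in the documents supports that, given the exclusion of expected difficult airways and a single experienced operator. The issue is confined to one secondary outcome.
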